5.2 Randomized Intervention Study

Primary outcome

Proportion of patients prescribed an antibiotic in each arm by day 28.

The following information will be collected to assess the proportion of patients prescribed an antibiotic in each arm by day 28:

- Day of the antibiotic prescription
- Antibiotic substance prescribed
- Dosage of antibiotic prescribed
- Duration of the antibiotic treatment prescribed

Secondary Outcomes

Clinical outcomes

- a. Duration of the episode: number of days during which the patient was symptomatic (defined by the daily symptom diary and telephone follow-up) within 28 days of follow-up.
- b. Duration of restricted daily activities: number of days during which the patient's daily activities (work or recreation) were restricted due to a respiratory tract infection.
- c. Clinical failure by day 7:
 - i. Admission to hospital within 7 days of follow-up
 - ii. Death within 7 days of follow-up
 - iii. No amelioration or worsening of relevant symptoms (fever and/or dyspnoea) at day 7
- d. Number of medical visits for the episode of LRTI within 28 days of enrolment.
- e. Serious adverse outcome: measured by day 28, based on the advent of at least one of the following events:
 - i. Death
 - ii. Secondary admission to hospital for any reason
 - iii. Complications (persistence of pneumonia, lung abscess, lung effusion, empyema or sepsis)
- f. Number of days with side effects related to antibiotics within 28 days of follow-up

The following information will be collected during telephone follow-up and recorded in the eCRF. It will also be obtained from the patient's diary.

Consultation process

- a. Median duration of time spent for the medical consultation, blood sampling, PCT measurement, lung US and total time spent in the practice.
- b. Quality of the ultrasound images. Agreement between GPs and experts on ultrasound images interpretation.
- c. Evaluation of the satisfaction of providers and of patients.

Economic aspects

- a. Cost / effectiveness ratio expressed as amount of money required per 1% absolute decrease of the proportion of antibiotic prescription.

Exploratory Outcomes

- a. Prevalence of different respiratory pathogens assessed by multiplex rt-PCR on nasopharyngeal swab and sputum
- b. Sensitivity and specificity of combinations of host biomarkers and gene expression signatures in identifying patients with serious adverse outcome, clinical failure or with pneumonia

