8. STUDY INTERVENTION

8.1 Identity of Investigational Products

There are no investigational products used in this study, as PCT and ultrasound are 2 recognised

diagnostic methods for pneumonia. The trial interventions consist of the UltraPro algorithm (Intervention 1) and of the PCT only arm (Intervention 2).

We did not include an additional arm testing lung ultrasound alone as the PCT rule-in test to decide on lung ultrasonography will decrease the number of patients who need to undergo ultrasound, which is time-consuming and will be easier to implement at large scale in GP practices.

This is a three-arm intervention study (Figure 3):

- Arm 1 (UltraPro): Management based on sequential testing of PCT and lung ultrasonography
- Arm 2 (PCT): Management based on PCT result only
- Arm 3 (control): Usual care

Experimental Intervention (treatment / medical device)

Arm 1: UltraPro

GPs randomly assigned to the UltraPro arm will be responsible to recruit patients fulfilling the inclusion criteria and manage them using the UltraPro algorithm. This is also the arm evaluated during the pilot study.

The UltraPro algorithm combines the result of a PCT point-of-care test with lung ultrasound result to decide on antibiotic prescription. Other inflammatory biomarkers, such as CRP, will not be used in this arm.

GPs in this group will also receive detailed training (described in section 8.2.1) on the epidemiology and management of pneumonia in Switzerland as part of the intervention.

First, PCT will be measured using the portable Thermo-Fisher© PCT Direct rapid point-of-care test provided by the study team. This immunoassay provides a quantitative PCT result in 20 minutes using 20 µL of whole blood. This new device has been validated by comparison with the reference method (Thermo-Fisher, personal communication excellent correlation index, $r^2=0.95$). The PCT threshold to decide on doing a lung ultrasonography has been chosen according to previous reports showing the safety of using a cut-off of 0.25 µg/L to decide on antibiotics prescription in case of acute respiratory infection at primary care level [13, 23, 24].

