In case of elevated PCT result ($\geq 0.25 \mu\text{g/L}$), a lung ultrasound will be performed to look for the presence of a lung infiltrate or consolidation suggesting the presence of CAP (Figure 3). Lung ultrasonography using the Phillips© Lumify portable ultrasound with a L12-4 (convex) transducer will be performed. The ultrasound will be provided to the GPs by the study team.

The lung ultrasound will be done following international evidence-based recommendations for point-of-care lung ultrasound using a ten points sonographic technique and the criteria for positive scan and positive examination for the diagnosis of pneumonia [39, 40]. The lung ultrasound is expected to last for 15 minutes.

Antibiotics will be prescribed only if a lung infiltrate or consolidation is identified during lung US. The choice, dosage and duration of antibiotic treatment will be left to the discretion of the GP.

Naso-pharyngeal swabs and venous blood samples will be systematically collected for further exploratory analysis. Sputum will also be collected if the patient is able to produce it.

Arm 2: PCT

GPs randomly assigned to the PCT arm will be responsible to recruit patients fulfilling the inclusion criteria and manage them using the PCT result.

GPs in this group will also receive training detailed training (described in section 8.2.1) on the epidemiology and management of pneumonia in Switzerland as part of the intervention.

The PCT point-of-care test will be performed, as described above, to decide on antibiotic prescription. Antibiotics will be prescribed only in case of elevated PCT ($\geq 0.25 \mu\text{g/L}$) (Figure 3). The choice, dosage and duration of antibiotic treatment will be left to the discretion of the GP.

Naso-pharyngeal swabs and venous blood samples will be systematically collected for further exploratory analysis. Sputum will also be collected if the patient is able to expectorate.

Control Intervention (standard/routine/comparator treatment / medical device)

Arm 3: usual care arm

GPs randomly assigned to the usual care arm will be responsible to recruit patients fulfilling the inclusion criteria and will manage and treat these patients as they usually do (Figure 3). They will not receive any additional training.

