	Post-training testing	
Test: Questionnaire on updated general knowledge
 
Test evaluating image acquisition on a healthy volunteer (duration of the exam and quality criteria)
 
Test evaluating image interpretation using existing images
 
Learning objectives: proportion of 95% of good quality images acquisition and 90% of interpretation agreement with the expert
 
In case objectives are not achieved, an extra half-day training will be offered. If the second test evaluation does not reach learning objective, the GP will be excluded of the study.

	Practical training	
Training in using the standard lung ultrasound procedure.
 
Direct supervision of lung ultrasonography on selected cases to improve image acquisition and interpretation.

Table 1: Training curriculum of GPs.

Before starting the study, a face-to-face visit of the GP at his own practice will be done. The medical assistant will be trained in the screening procedure and in PCT measurement.

Arm 2- PCT

A training program for physicians and medical assistants recruited in the PCT arm will be performed.

The training will be the same as described above in table 1 except for lung ultrasonography. GPs will have half day training corresponding to the morning of day 1.

Before starting the study, a face-to-face visit of the GP at his own practice will be done. The medical assistant will be trained in the screening procedure and in PCT measurement.

Control Intervention

Before starting the study, a face-to-face visit of the GP at his own practice will be done. The medical assistant will be trained in the screening procedure and in performing naso-pharyngeal swabs and collecting sputa.

There will be no training program for physicians and medical assistants recruited in the “usual care” arm. This is a deliberate choice as the detailed training on local epidemiological data, antibiotic resistance and guidelines for the management of LRTI and pneumonia is part of the experimental intervention. Giving this training to GPs in the “usual care” could lead to reduced inappropriate antibiotic prescription.

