Transcripts will be read to identify abstract themes relating to the meaning of the text. After the identification of the main themes, these will be developed in a coding scheme that will be applied to the text. The codes will then be applied to the text of in an independent fashion by two different investigators. Software designed for qualitative analysis (QDA Miner[©] or Atlas.ti[©]) will be used.

Quantitative data

Quantitative data relating to the study processes will be obtained by questionnaires designed to assess different steps of the study process.

Clinical data will be collected as per protocol for the randomized trial

Randomized trial

All study participants will undergo clinical and laboratory evaluation at inclusion (Day 0) according to the arm to which they are allocated. The following data will be collected:

Clinical data collection

A short electronic case report form (eCRF) will be filled by the GP on a tablet computer provided by the study team. Data collected include demographic characteristics, medical history, symptoms and clinical examination findings. Whether or not the GP ordered supplementary tests for the management of the patient outside the scope the algorithm will be recorded.

Ultrasonographic (UltraPro arm) data collection

All US images captured will be digitally recorded and transferred via a secured internet connection along with relevant metadata to a secure server. For study quality control purposes, the quality of the image and the interpretation of a random sample of images will be evaluated retrospectively by an experienced radiologist.

Laboratory specimen collection

Blood samples

In the UltraPro and PCT arms, a total of 17.5 mL of whole venous blood will be drawn to perform the PCT POCT measurement and for the exploratory objectives.

50 µL of whole blood will be used for the POCT PCT measurement. The rest of the sample will be used for identification of novel host biomarkers and genetic (identification of SNPs in genes that regulate microvascular integrity and transcriptomics) analyses that will be done in batch after the completion of the study. This will be performed at the Sandra Rotman Laboratory in Ontario, Canada

The following table describes the nature of the biological sampling:

Tube	Volume	Storage	Aim
EDTA 7.5 ml	20µL of whole blood	None	POCT PCT measurement
	3 x 1000 µL of whole blood	-80°C	SNPs analysis Biobank
EDTA 7.5 ml	3 x 1000 µL of plasma	-80°C	Novel host biomarkers Biobank

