11.2 Determination of Sample Size

The sample size was calculated to assess a decrease in antibiotic prescription of at least 15% between the UltraPro and the PCT arms as well as 15% between the PCT arm and usual care.

The proportion of patients receiving antibiotics with the usual care is estimated to be around 60% and to decrease to 45% using PCT and to 30% combining PCT and ultrasound. These numbers have been extrapolated from the subgroup of patients with LRTI in a study at primary care level in the Netherlands [3].

A study sample of 14 GPs and 15 patients per GP in each arm (210 patients per arm and a total of 630 patients) gives a power of 80% to detect a decrease in antibiotic prescription from 60% (usual care) to 45% (PCT), and from 45% (PCT) to 30% (UltraPro), with 5% level of significance, when adjusting for clustering at practice level (intracluster coefficient 0.06) [3]. This sample size guarantees a power of 80% to prove non-inferiority in terms of duration of activities restriction (non-inferiority margin=1 day, standard deviation=4 days) as well as of composite adverse outcome (probability in the “usual care” arm 0.05 with a non-inferiority margin of 0.02). Simulations used to determine the sample size are shown in the following figures.

[figure not shown]

Figure 4: Statistical simulations used to determine sample size

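### GP-expert agreement on lung ultrasound is a secondary outcome, but only an unspecified random sample of images is re-read and no agreement analysis is planned; reading every examination would be cheap and would measure the right thing

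*Combined protocol and SAP*

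**What the plan says.** Section 5.2 of the combined protocol and SAP puts image quality and "Agreement between GPs and experts on ultrasound images interpretation" among the secondary outcomes, under the consultation process. The outcome list in the synopsis omits it.

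Section 9.2 refers to section 8.5 for how outcomes are assessed. There, under ultrasonographic data collection, "All US images captured will be digitally recorded and transferred via a secured internet connection", but "the quality of the image and the interpretation of a random sample of images will be evaluated retrospectively by an experienced radiologist". The stated purpose is study quality control. No fraction, number, sampling unit or stratification is given, and nothing is said about what the radiologist knows when reading. Section 11.4 (planned analyses) has no analysis of agreement.

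Ultrasound is used only in the UltraPro arm and only after a raised PCT. Section 8.1 gives the reason: "the PCT rule-in test to decide on lung ultrasonography will decrease the number of patients who need to undergo ultrasound". The examination covers ten scanning points, and the antibiotic decision follows from whether it shows an infiltrate or consolidation.

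The training table in section 8.2 sets the learning objective: "proportion of 95% of good quality images acquisition and 90% of interpretation agreement with the expert".

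**The concern.** Three things do not fit together.

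- **Outcome and data source.** A listed secondary outcome rests on a quality-control sample of unknown size, and no estimand or analysis is attached to it.
- **Small pool.** The PCT step limits the number of scans, so taking a sample discards information where there is little to begin with.
- **Unit.** The GP makes one call per examination. Agreement on individual images is a different quantity: a GP and an expert can agree on most images and still differ on whether the patient has pneumonia. Several images from one patient are also correlated.

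At stake is how the comparison of UltraPro with PCT is interpreted. Under adherence, the planned fall from 45% to 30% comes entirely from patients with raised PCT whose scan the GP reads as negative. The same readings carry the risk named in section 3.4, that antibiotics are withheld from patients with pneumonia. If the trial succeeds or fails on this step, readers will want to know how often those negative readings were confirmed.

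**Working it through.** The plan gives no expected number of scans and no precision for agreement, so there is no figure of its own to reproduce.

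**Inputs from the documents**

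- UltraPro arm: 14 GPs x 15 patients = 210 (11.2).
- Planned prescribing: 60% under usual care, then "to decrease to 45% using PCT and to 30% combining PCT and ultrasound" (11.2).
- PCT arm: "Antibiotics will be prescribed only in case of elevated PCT" (8.1). With adherence, prescribing in that arm is about the share with raised PCT.
- UltraPro arm: antibiotics only after a positive scan (8.1). With adherence, every treated patient has been scanned.
- Prescribing under PCT guidance in the two cited primary-care trials: 21.5% and 25% (3.1). These are proxies from trials of acute respiratory infection in general.
- Agreement level for illustration: 90%, the training target (8.2).

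**Expected scans**

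- From the 45% rate: 210 x 0.45 = 94.5, about 95 scans, or 6.75 per GP.
- From the 30% rate: 210 x 0.30 = 63 positive scans, so at least 63 scans, or 4.5 per GP.
- From the cited trials: 210 x 0.215 = 45.2 and 210 x 0.25 = 52.5 scans, or about 3 to 4 per GP.

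The protocol's own planning range is therefore about 63 to 95. The figure of 45 is a low scenario.

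**Precision of overall agreement**

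These are exact (Clopper-Pearson) 95% intervals, with no allowance for clustering. The re-read fractions are assumptions, since the plan states none, and the table treats the sampled unit as an examination.

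| Pool of scans | Fraction read | Agree / read | 95% CI |
|---|---|---|---|
| 45 | 20% | 8/9 | 52-99.7% |
| 45 | 50% | 20/22 | 71-99% |
| 45 | 100% | 40/45 | 76-96% |
| 63 | 20% | 12/13 | 64-99.8% |
| 63 | 50% | 29/32 | 75-98% |
| 63 | 100% | 57/63 | 80-96% |
| 95 | 20% | 17/19 | 67-99% |
| 95 | 50% | 43/48 | 77-97% |
| 95 | 100% | 86/95 | 83-96% |

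**Clustering, all scans read**

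The design effect is 1 + (N/14 - 1) x ICC. Applying the ICC of 0.06 from section 11.2 to agreement (an assumption) gives 1.13, 1.21 and 1.35 for N = 45, 63 and 95. Wilson intervals at exactly 90% on N divided by the design effect are 77-96%, 79-96% and 81-95%. Clustering widens the intervals only slightly, because each GP performs few scans.

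**GP-negative scans after raised PCT**

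At the planning rates these number 94.5 - 63 = 31.5, about 32.

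| Fraction read | GP-negative scans read | Example | 95% CI |
|---|---|---|---|
| 20% | about 6 | 5/6 | 36-99.6% |
| 50% | about 16 | 14/16 | 62-98% |
| 100% | about 32 | 29/32 | 75-98% |

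**The case against.** A reader might infer that agreement will be almost unestimated. The documents do not support that, because they state no sampling fraction. The very wide intervals come from an assumed fraction of about a fifth; half of a pool near 95 already gives 77-97%.

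A reader might also infer that a few dozen scans cannot separate 90% agreement from 60-70%. They can: 27/30 gives 73.5-98%, which excludes both values. Even 17/19 (67-99%) excludes 60%.

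The range of 45 to 95 scans should not be read as a limit. It uses prescribing as a stand-in for PCT positivity. Its lower end comes from a trial in which only 36% of patients had a lower respiratory tract infection, and it conflicts with the 63 or more scans implied by the planned 30%. The algorithm is re-applied at follow-up visits (8.5) and GPs may modify the intervention (8.3), so further scans are possible.

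Sampling by image could touch more examinations than the same fraction of examinations would, given ten scanning points. That weakens the arithmetic for small fractions, but it does not turn image agreement into agreement on the decision.

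Reading skill is also addressed elsewhere. The pilot of 30 consultations scans patients whatever their PCT and compares the GP's reading with that of a blinded radiologist (5.1, 6.1). A GP in the UltraPro arm who misses the training objectives twice is excluded, and a four-hour refresher is planned (8.2). These safeguards are real, but none of them measures agreement on trial patients.

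Finally, reading accuracy cannot be called the main explanation of the trial's result: PCT positivity and adherence are rivals. Agreement is a process outcome and does not enter the primary analysis.

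**Conclusion.** The point holds as a cheap improvement. A listed secondary outcome depends on a sample whose fraction, unit and blinding are unstated, and it has no planned analysis. The plan samples images, whereas the decision is made per examination.

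The gain in precision depends on the fraction the team has in mind. Compared with a fifth of the scans, a full read narrows the interval from 67-99% to 83-96% for a pool of 95, and from 64-99.8% to 80-96% for a pool of 63. Compared with half of a pool of 95, the gain is modest (77-97% to 83-96%). It matters most for the roughly 32 GP-negative scans, where even a full read gives only 75-98%.

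These figures assume adherence to the algorithm, planned prescribing as a proxy for PCT positivity, agreement near 90%, and no clustering except where shown.

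**What to change.** In section 8.5, replace the sampled read by a read of every lung ultrasound examination by the radiologist already planned, blind to the GP's reading and to PCT. The pilot reader in section 5.1 is already blinded to patient characteristics and to the GP's interpretation. A scan done per algorithm itself signals a raised PCT, so in practice it is the PCT value that is withheld.

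In section 11.4, define agreement per examination (pneumonia yes or no). Report it overall and separately for GP-negative and GP-positive scans, with confidence intervals that allow for clustering by GP. State how repeat scans of one patient are counted. If sampling is kept, sample examinations rather than images, state the number, and justify it by the precision it gives.

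The cost is a few dozen more retrospective reads of images already stored, with no new reader, no patient contact and no change in care. Precision will still be modest overall and low for any single GP, at roughly 3 to 7 scans each.

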8.6 Trial specific preventive measures

Not applicable

8.7 Concomitant Interventions (treatments)

Concomitant interventions related to the study intervention are permitted in all arms. Their use will be recorded in the eCRF. They include:

- Additional diagnostic studies (chest X-ray, C-reactive protein, full blood count, etc...)
- HIV testing
- Prescription of additional treatments (ie. bronchodilatators, anti-inflammatory drugs, paracetamol, nasal decongestants)
- Prescription of chest physiotherapy

8.8 Study Drug / Medical Device Accountability

Not applicable

8.9 Return or Destruction of Study Drug / Medical Device

Not applicable

9. STUDY ASSESSMENTS

9.1 Study flow chart(s) / table of study procedures and assessments

Visit	Inclusion	Follow-Up	Unplanned visit or worsening condition
Day	0	7	28
Patient consultation with GP	X		X
Phone interview with patient by the study team		X	X
Patient Characteristics			
Patient Information and Consent	•		
Inclusion/Exclusion Criteria	•		
Demographics	•		
Relevant Medical History	•		•
Vital Signs/Clinical Examination	•		•
Laboratory Results and treatments	•		•
Study Interventions			
PCT Arm POCT PCT	•		•
UltraPro Arm POCT PCT	•		•
Lung Ultrasound	•		•
Outcomes			
Antibiotic prescription	•		•
Duration of the episode		•	•
Adverse effects from antibiotics		•	•
Clinical failure		•	•
Serious Adverse Outcome		•	•
Process Efficacy and Satisfaction	•	•	•
Reminder to fill symptoms diary	•	•	
Biological sampling			
Naso-pharyngeal swab	Multiplex rtPCR for respiratory pathogens	•	•
Sputum			
Blood sampling			
EDTA 2 x 7.5 ml	POCT PCT and Biomarkers, SNPs and biobank	•	•

9.2 Assessments of outcomes

Assessment of primary outcome

Pilot Study

Assessment of the outcomes of the pilot study has been described in section 8.5.1.

Randomized intervention study

Assessment of the outcomes of the randomized intervention study has been described in section 8.5.2.

Assessment of secondary outcomes

Pilot Study

Assessment of the outcomes of the pilot study has been described in section 8.5.1.

Randomized intervention study

Assessment of the outcomes of the randomized intervention study has been described in section 8.5.2.

Assessment of other outcomes of interest

Assessment of the exploratory outcomes has been described in section 8.5.2.3

Assessment of safety outcomes

Adverse events

The GP will be asked to record any serious adverse events (hospitalization, death) within 7 days into the eCRF. Any new recording of severe adverse events (SAE) will be automatically notified to the PI. Adverse events recorded by telephone follow-up will also be recorded

Laboratory parameters

In the intervention arms, prescription of laboratory tests (other than PCT POCT) will be at the discretion of the participating physicians. They will follow their usual routine, either for tests performed in house or sent to an external laboratory. No additional quality control or standard procedures are planned for this aspect.

Vital signs

Vital signs will be assessed with the usual equipment available to the GP at his practice. Measurement is expected to reflect routine practice, and as such no standardized measurement protocol or calibration procedures are planned.

Assessments in participants who prematurely stop the study

Patients will be considered lost to follow-up if telephone interviews were not feasible. A patient may change GP over the course of the study, without this affecting his participation in the study. Phone interviews will continue.

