An individual patient may also choose to refuse the phone interview, without discontinuing the study itself. In this case, the investigators can access the medical file until the end of the 28 days observation period.

There are no foreseeable reasons for investigators to withdraw a patient from the study. Patients who are not reachable during follow-up will not have outcome data. They will be excluded from the analysis of the safety of the intervention but they will still be included in the assessment of impact on antibiotic treatment and of the feasibility of the intervention.

Physicians may choose to discontinue participating in the study. If so, they are responsible of informing the study team. If discontinuation occurs before the training and randomisation session, they will be replaced by another willing physician. If discontinuation occurs after patient recruitment, training and randomisation, patient outcomes will be collected by the study staff until the end of planned follow-up. Access to the medical files will be discussed on a case by case basis with the physician.

There is no foreseeable reason for the investigators to withdraw a physician from the study once he participated in patient recruitment, training and randomisation.

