PaxGene	2.5 ml	-80°C	Transcriptomics

Table 2. Details of blood samples collected in the study

Naso-pharyngeal swabs

For future analyses, a naso-pharyngeal swab will be performed on all patients recruited in the study. A eSwab™ (Copan Diagnostics[©]) will be introduced in the nasal cavity until the naso-pharynx in one

nostrils. Swabbing will then be performed. The sample will then be conserved at -80°C using a liquid collection and transportation system.

A respiratory pathogen multiplex real time polymerase chain reaction (PCR) assay will be retrospectively performed in the laboratory of virology of Geneva University Hospital to identify the aetiological agent of the LRTI. Such an approach has been described in other studies [41].

Sputa

For future analyses, a sputum sample will be collected for all patients recruited in the study if they are able to produce it. The sample will then be conserved at -80°C.

A respiratory pathogen multiplex real time PCR assay will be retrospectively performed in the laboratory of virology of Geneva University Hospital and culture will be performed in the microbiology laboratory of Lausanne University Hospital to identify the aetiological agent of the LRTI.

Follow-up after initial assessment

Active surveillance

All participants will be contacted by phone at day 7 and day 28 by the study team.

At days 7 and 28, a standardized interview will be done to ensure that the patient is alive, to:

- evaluate clinical outcome (presence or recurrence of LRTIs symptoms)
- record any additional visits
- record additional antibiotic prescription
- record number of days during which daily activities (work or recreation) were restricted
- evaluate antibiotic side effects
- record secondary hospital admission
- patient satisfaction will be recorded at day 28 only

The caller will be blinded as to the arm in which the patient was included.

All participants will be asked to fill a daily diary until symptom resolution up to day 28. The diary can be filled in paper and returned by post or for participants who prefer an electronic version will be made available.

They will report each day on 6 items:

- coughing
- phlegm
- shortness of breath
- sleep disturbance
- impairment of normal daily activities
- generally feeling unwell

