10.2 Reporting of serious adverse events (SAE) and other safety related events

If serious adverse events occur, and it cannot be excluded that the events are attributable to the intervention under investigation, the GP must document them in a standardised manner. In addition, the GP shall report these events to the Principal-Coordinating investigator within 24 hours, who will report them to the competent ethical committee within 15 days.

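### The serious adverse outcome runs to day 28, but GP recording of deaths and admissions is tied to 7 days, and two contradictory rules classify patients who cannot be interviewed

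*Combined protocol and SAP*

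**What the plan says.** **Endpoint.** Section 5.2 defines the outcome thus: "Serious adverse outcome: measured by day 28, based on the advent of at least one of the following events". The events are death, any later hospital admission and a list of complications. Clinical failure is a separate endpoint that ends at day 7; one of its components is "Admission to hospital within 7 days of follow-up".

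**Recording by the GP.** Section 9.2, under safety outcomes: "The GP will be asked to record any serious adverse events (hospitalization, death) within 7 days into the eCRF". It adds: "Adverse events recorded by telephone follow-up will also be recorded".

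**Scheduled contact.** Section 8.5: "All participants will be contacted by phone at day 7 and day 28 by the study team". The interview is meant to establish that the patient is alive and to record admissions.

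**Patients who cannot be interviewed.** Section 9.2: "Patients will be considered lost to follow-up if telephone interviews were not feasible". Section 7.2: "Patients who are not reachable during follow-up will not have outcome data"; it then removes them from the safety analysis. Section 11.4, on analysis populations, instead counts patients lost to follow-up as clinical failures with an adverse outcome.

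**The concern.** The window of the endpoint and the wording of the GP instruction do not match. The 7 days could run from enrolment, which suits clinical failure but not the day-28 outcome. They could also be the time allowed for entering an event, and section 11.4 does use seven days as a reporting deadline to the steering committee. The text does not settle it.

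On either reading there is a second gap. Being reachable by phone on day 28 depends on the outcome: a patient who has died, or is in hospital that day, is less likely to be interviewed. The plan describes no contact with relatives, no hospital enquiry and no check of the GP's records for a patient who does not answer.

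Section 3.4 names wrongly withheld antibiotics in pneumonia as the potential risk. There is no data safety monitoring committee (1.6), and early termination on safety grounds rests on interim results reviewed by the steering committee (2.9, 11.4). The safety conclusion therefore depends on knowing who died or was admitted.

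**Working it through.** **1. The plan's own figure for this endpoint.** Section 11.2 states 80% power for non-inferiority on the composite, with 5% in usual care, a 2-point margin and 210 patients per arm. With equal true rates, n per arm = (z₁₋α + z₀.₈₀)² × 2 × 0.05 × 0.95 / 0.02².

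- One-sided α = 0.025: (1.960 + 0.842)² × 0.095 / 0.0004 ≈ 1,865. One-sided α = 0.05: 1,469. Both are before clustering.
- Power at 210 per arm: 15% and 24%. With design effect 1 + 14 × 0.06 = 1.84 (210 / 1.84 = 114 effective patients): 10% and 17%.

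The 80% is not reproduced. The simulations in Figure 4 are not visible and may use unstated assumptions. That is a separate matter, and nothing below relies on the 80%.

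**2. Sources for an event on days 8 to 28.**

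| Source | Section | Limit |
|---|---|---|
| GP record of admission or death | 9.2 | 7 days, start of the clock not stated |
| Day-28 interview | 8.5, 9.3 | Needs a patient who can be interviewed |
| Symptom diary | 8.5 | Filled in by the patient; six symptom and function items; ends at resolution |
| GP form at a visit for deterioration | 8.5, passive surveillance | No day limit, but needs a return to the GP; 3.4 also points patients to emergency centres |
| SAE reporting by the GP | 10.1–10.3 | No day limit, but GP documentation is required where "it cannot be excluded that the events are attributable to the intervention under investigation", and the GP must know of the event |
| Medical file to day 28 | 7.2 | Given only for patients who decline the interview |

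Only the interview is both scheduled for every patient and able to show an admission after day 7.

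**3. One patient followed through the rules.** Take a patient admitted through an emergency centre on day 20 who has died, or is still in hospital, at the day-28 call.

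- 9.2: the interview is not feasible, so the patient is lost to follow-up.
- 7.2: no outcome data, excluded from the safety analysis. A true event disappears.
- 11.4: counted as an adverse outcome. The event is kept, but a patient who is well and does not pick up the phone is also counted.

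The same patient gets opposite treatment, and neither rule asks what happened.

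**4. Scale.**

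- Expected events per arm: 0.05 × 210 = 10.5.
- Margin in patients per arm: 0.02 × 210 = 4.2.
- Events after day 7, if that share is 25% to 75% (assumption): 2.6 to 7.9 per arm. These are exposed to the weaker sources, not lost.
- Events lost under 7.2, if 25% to 100% of those are missed (assumption): 0.7 to 7.9 per arm, an observed rate between 4.7% and 1.3%. The upper end means that every source in the table fails.
- False events under 11.4: event-free patients number 210 × 0.95 = 199.5. If 1%, 2% or 5% of them are not reached (assumption), 2.0, 4.0 or 10.0 per arm are added.

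**5. What this does to the comparison.** The margin applies to the difference between arms. If a fraction L of events is lost equally in both arms, a true difference d is observed as about d × (1 − L); a 2-point difference with L = 0.25 appears as 1.5 points. If a fraction r of event-free patients is falsely counted in both arms, the difference becomes d × (1 − r). Equal misclassification shrinks a difference rather than shifting it. A shift needs unequal misclassification, which the documents do not show.

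**The case against.** The strongest reply has four parts.

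- **The 7 days may be an entry deadline.** The next sentence in 9.2 concerns automatic notification, and 11.4 uses the same interval as a deadline. This stands as a possible reading: a day-7 cut-off for GP recording is not established. It leaves the non-responder gap open.
- **Other sources exist.** A reader might infer that days 8 to 28 rest on the phone call alone. The documents do not support that: the deterioration form and the SAE sections carry no day limit, GPs follow known SAEs to resolution, and the file is open for those who decline the call. In a trial of withholding antibiotics, many respiratory admissions would be hard to call unrelated. But each route is conditional, and none is triggered by an unanswered call.
- **Most hospitalised patients can still report.** The day-28 interview looks back, so a patient discharged before the call can report the admission. This stands. The gap concerns deaths not learned of otherwise, patients still in hospital, and other non-responders.
- **Section 11.4 already counts lost patients as events.** True under that section, so a late death is not necessarily dropped. But 7.2 says the opposite, and 11.4 adds false events.

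A reader might also set the late events (2.6 to 5.3 per arm at an assumed 25% to 50% share, or 1.3 to 2.5 points) directly against the 2-point margin. That does not follow: these are all late events, not lost ones, and the margin concerns a difference between arms that share the same phone schedule and a blinded caller.

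**Conclusion.** The concern holds in this form: the 7-day wording does not fit the day-28 endpoint and is ambiguous; the day-28 interview is the only scheduled ascertainment after day 7; and patients who cannot be interviewed fall under two contradictory rules, neither based on their true status. Followed literally, 7.2 can remove a death or a continuing admission because of the outcome itself.

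As to size, the documents support only the frame: 10.5 expected events and a margin worth 4.2 patients per arm, both resting on the plan's 5% rate and full recruitment. Misclassifying a handful of patients is therefore not negligible. The number lost, and any bias between arms, cannot be derived; the ranges above rest on assumed shares.

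The endpoint is secondary, and 7.2 keeps unreachable patients in the antibiotic analysis. The change should be made because it is cheap and protects the safety conclusion.

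**What to change.** - **9.2, safety outcomes:** state that GP recording of death, hospital admission and the listed complications covers events up to day 28. Give any entry deadline separately and say what starts its clock.
- **5.2, 7.2 and 9.2:** make the GP entry or the medical file the source for these components whenever the call fails, whether through refusal, no answer, death or admission. A patient whose status is known this way is not lost to follow-up for them.
- **7.2 and 11.4:** choose one rule for patients whose status stays unknown, state it in both places, and report their number by arm. The other handling can serve as a sensitivity analysis.

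Cost: one short GP eCRF entry at day 28, the wording changes, and confirmation that consent covers file access for non-responders, since 7.2 now gives it only for those who decline the call. A residual gap may remain for patients who change GP, which 9.2 allows.
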